## 9.2 Sample Size Determination

Approximately 212 participants will be enrolled to achieve approximately 146 participants randomly assigned to study intervention.

Randomisation will be stratified by average baseline PAINS-pNF chronic target PN pain score and geographical region. The number of participants randomised will be capped at approximately 106 participants with an average baseline PAINS-pNF chronic target PN pain score  $\geq 3$  and approximately 40 participants with an average baseline PAINS-pNF chronic target PN pain score  $< 3$ .

Enrolled	Estimated 212 participants
Randomly assigned	Selumetinib: Estimated 73 participants Placebo: Estimated 73 participants

Note: "Enrolled" means a participant's agreement to participate in a clinical study following completion of the informed consent process. Potential participants who are screened for the purpose of determining eligibility for the study, but are not randomly assigned in the study, are considered "screen failures", unless otherwise specified by the protocol.

With a sample size of 73 participants per arm, a Fisher's Exact Test with a two-sided alpha of 5% will have >99% power to detect the difference between selumetinib ORR of 20% and placebo ORR of 0%. The ORR of 20% in the selumetinib arm by end of Cycle 16 is assumed from ad hoc modelling performed using the SPRINT NCI and ICR data and the Adult NF1 NCI study response rates. The ORR of 0% in the placebo arm is assumed because at the end of Cycle 16, participants randomised to placebo will only have received 4 cycles of selumetinib post-crossover, therefore any response detected post-crossover at end of Cycle 12 will be unconfirmed. Spontaneous shrinkage  $\geq 20\%$  during the first 12 cycles of placebo treatment is also not expected ([Akshintala et al 2020](#)).

Forty-two participants per arm are required for the study to have 90% power to detect a treatment difference of  $\geq -2$  in the 1st key secondary endpoint change from baseline of PAINS-pNF chronic target PN pain score (assuming an SD of 2.8) in favour of selumetinib compared with placebo at a two-sided alpha level of 5%. To allow for approximately 20% drop out (ie, participants without at least one postbaseline average cycle PAINS-pNF chronic target PN pain score), 106 participants with a baseline PAINS-pNF chronic target PN pain score of  $\geq 3$  will be randomised in a 1:1 selumetinib: placebo allocation. There is no formal sample size calculation regarding randomising 40 participants with baseline PAINS-pNF chronic target PN pain score of  $< 3$ ; however, this is deemed sufficient to ensure the target population of adults

with NF1 and symptomatic, inoperable PN (including those with little or no baseline PN pain) are represented.

By assuming a 20% drop out (i.e, participants without at least one post baseline PlexiQoL total score), 58 participants per arm will provide at least 80% power to detect a treatment difference at Cycle 12 in the 2nd key secondary endpoint change from baseline of PlexiQoL total score (assuming an SD of 2.3) of at least -1.2 in favour of selumetinib compared with placebo at a two-sided alpha level of 5%. Refer to Table 11. to some scenarios for the statistical power for the 2nd key secondary endpoint with different mean difference in the change from baseline of the PlexiQoL total score at Cycle 12 between the two treatment groups. This range of possible treatment effects for selumetinib that could be observed in a multinational population was extrapolated based on the differences observed in other HRQoL scores in other rare disease studies as compared to an Adult selumetinib cohort (Study D1346C00011).

**Table 11 Scenarios for the power of the second key secondary endpoint**

Mean Treatment Difference	Statistical Power
-0.7	37%
-0.8	47%
-0.9	56%
-1	65%
-1.1	73%
-1.2	80%
-1.3	86%
-1.4	91%
-1.5	94%
-1.6	96%
-1.7	98%

If it is anticipated that 20% or more of participants (across blinded study intervention groups) withdraw prior to the end of Cycle 16, for reasons other than progression, then recruitment rates notwithstanding, enrolment will continue to randomise at least 50% of the total number of drop-out participants to ensure the primary endpoint is adequately powered.

### **9.3 Populations for Analyses**

The following populations are defined:

**Table 12** **Populations for Analysis**

Population/analysis set	Description
Enrolled	All participants who sign the ICF.
FAS	All participants who are randomised to study intervention in the study. Treatment groups will be compared on the basis of randomised study intervention, regardless of the study intervention actually received. Participants who were randomised but did not subsequently receive study intervention are included in the analysis in the treatment group to which they were randomised.
Measurable PN FAS	All participants who are randomised to study intervention in the study with measurable target PN at baseline per ICR. Treatment groups will be compared on the basis of randomised study intervention, regardless of the study intervention actually received. Participants who were randomised but did not subsequently receive study intervention are included in the analysis in the treatment group to which they were randomised.
Pain FAS	All participants with a baseline PAINS-pNF chronic target PN pain intensity score $\geq 3$ . Treatment groups will be compared on the basis of randomised study intervention, regardless of the intervention actually received. Participants who were randomised but did not subsequently receive study intervention are included in the analysis in the treatment group to which they were randomised.
Selumetinib FAS	All participants who are randomised to selumetinib with measurable target PN at baseline per ICR and who have received at least one dose of selumetinib.
Extended selumetinib FAS	All participants who are randomised to study intervention in the study with measurable target PN at baseline per ICR and who have received at least one dose of selumetinib, ie including participants randomised to placebo who crossover to selumetinib treatment.
Safety analysis set	The Safety analysis set will consist of all enrolled participants who received any amount of study intervention. Safety data will be summarised according to the treatment received.
PK analysis set	All participants assigned to study intervention who take at least one dose of study intervention for whom any post-dose reportable PK concentration is available and who do not violate or deviate from the protocol in ways that would significantly affect the PK analyses.
Fed measurable PN FAS	All participants who are randomised to study intervention in the study with measurable target PN at baseline per ICR, who have received at least one dose of selumetinib in fed state (i.e participant can eat at any time point in relation to each selumetinib intake without continuing to observe the fasting restriction after the end of Cycle 24) and who have at least one evaluable scan per ICR assessment in fed state at end of Cycle 30 or later. Refer to Section 5.2.1 for the definition of participant fed state.

## 9.4 Statistical Analyses

The SAP will be finalised prior to DCO1 database lock and it will include a more technical and detailed description of the statistical analyses described in this section. This section is a

summary of the planned statistical analyses of the most important endpoints including primary and key secondary endpoints.

#### **9.4.1 General Considerations**

The below mentioned general principles will be followed:

Descriptive statistics will be used for all variables, as appropriate. Continuous variables will be summarised by the number of observations, mean, SD, median, upper and lower quartiles, minimum, and maximum. For log-transformed data it is more appropriate to present geometric mean, CV, median, minimum and maximum. Categorical variables will be summarised by frequency counts and percentages for each category.

Unless otherwise stated, percentages will be calculated out of the population total for the corresponding treatment group. Overall totals will be calculated for baseline summaries only.

Detail relating to handling the potential impact of COVID-19 on analyses will be detailed in the SAP.

For safety endpoints the last observation before the first dose of study intervention will be considered the baseline measurement unless otherwise specified.

The randomised period is defined as follows:

- For participants randomised to selumetinib: date of first dose of selumetinib until one day prior to date of Cycle 13 study intervention Day 1 or date of study intervention discontinuation (whichever occurs first).
- For participants randomised to placebo: date of first dose of placebo until one day prior to the date of first selumetinib intake (post crossover) or date of study intervention discontinuation (whichever occurs first).

Full details for handling missing data and definition of other study periods will be provided in the SAP.

#### **9.4.2 Efficacy**

##### **9.4.2.1 Primary Endpoint**

###### **9.4.2.1.1 Calculation of PN Assessment**

###### **Independent Central Review REiNS assessment**

The ICR will first determine the tumour volume (mL) of the target PN at the pre-treatment MRI using volumetric analysis. Then follow-up scans of the same target PN will be analysed to calculate the target PN tumour volume (mL) and percentage change in target PN volume from baseline.

For each participant, the target PN tumour response (CR, confirmed CR; PR, confirmed PR; stable disease or PD) at each post-baseline scan will be programmatically derived from the percentage change in target PN volume. If a participant has had a tumour assessment that cannot be evaluated, then the participant will be assigned a target PN tumour response of NE. This will be repeated for one non-target PN (if relevant).

Further details of the derivation of target PN tumour response, non-target PN tumour response and overall response will be detailed in the SAP.

#### **9.4.2.1.2 Objective Response Rate by end of Cycle 16**

The primary endpoint objective response rate is defined as the proportion of participants who have a confirmed CR (defined as disappearance of the target PN, confirmed by a consecutive scan within 3 to 6 months after the first response) or confirmed PR (defined as a target PN volume decrease  $\geq 20\%$ , compared to baseline, confirmed by a consecutive scan within 3 to 6 months after the first response) by end of Cycle 16 as determined by ICR per REiNS criteria.

The primary analysis will include all randomised participants with measurable target PN at baseline as determined by ICR (Measurable PN FAS). Any confirmed CR or a confirmed PR at or prior to end of Cycle 16 which occurred after a subsequent NF1-PN treatment (following study intervention discontinuation) will not be included in the numerator for the ORR calculation.

Supportive evidence of the primary endpoint of ORR by end of Cycle 16 will include:

- Changes in target PN volume (absolute and percentage change from baseline) over time in participants randomised to selumetinib and placebo. For participants randomised to placebo, these will include data prior and post selumetinib treatment initiation.

Full details of the derivation of ORR while on-treatment and supportive derivations will be documented in the SAP

#### **9.4.2.1.3 Analysis Methods**

The primary endpoint estimand is based on all randomised participants with measurable target PN at baseline per ICR (Measurable PN FAS).

Data obtained using on-treatment MRI volumetric assessments from first dose up until progression (if progression occurs prior to end of Cycle 16) or the last evaluable assessment up to and including end of Cycle 16 assessment in the absence of progression will be included in the primary endpoint assessment of ORR.

Participants who discontinue randomised treatment without progression, receive a subsequent NF1-PN therapy and then respond at or prior to end of Cycle 16 will not be included as

responders in the primary endpoint ORR by end of Cycle 16. Participants with no post-baseline MRI assessments up to and including end of Cycle 16 will be considered as non-responder (ie, not having a cCR or cPR).

Intercurrent events are addressed as follows:

- Post randomised study intervention discontinuation scans will not be included in the analysis assuming a while-on-treatment strategy to the intercurrent event of randomised study intervention discontinuation (including early crossover from placebo and progression) prior to end of cycle 16 due to any reason.
- Scans after the first 28 days of a prolonged study intervention interruption until study intervention has recommenced for at least 28 days will not be included in the analysis, assuming a while-on-treatment strategy to the intercurrent event of prolonged study intervention interruption (defined as a study intervention interruption greater than or equal to 28 days).
- Scans after target PN resection will be included in the analysis assuming a treatment policy approach to the intercurrent event of target PN resection.
- Scans after subsequent NF1-PN treatment will not be included in the analysis assuming a while-on-treatment strategy to the intercurrent event of subsequent NF1-PN treatment.

The primary endpoint ORR will be compared at the landmark end of Cycle 16 between selumetinib versus placebo using a Fisher's exact test. ORR by end of Cycle 16 in each treatment group will be presented with corresponding 2-sided exact 95% CI based on the Clopper Pearson method ([Clopper and Pearson 1934](#)). The risk difference and 95% CI based on the Miettinen-Nurminen (score) method ([Miettinen and Nurminen 1985](#)) will also be presented.

Change in target PN volume will be analysed using descriptive statistics and trajectory plots.

A supplementary analysis will be performed including all randomised participants (FAS).

Full details of the primary endpoint ORR analyses and supportive analyses will be documented in the SAP.

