## Statistical Methods

### Primary Estimand

The primary endpoint of ORR by end of Cycle 16 includes all randomised participants with measurable target PN at baseline as determined by ICR (Measurable PN FAS). The ORR is defined as the proportion of participants with measurable disease who have a confirmed CR (defined as disappearance of the target PN, confirmed by a consecutive scan within 3 to 6 months after the first response) or confirmed PR (defined as a target PN volume decrease  $\geq 20\%$ , compared with baseline, confirmed by a consecutive scan within 3 to 6 months after the first response) by end of Cycle 16 as determined by ICR per REiNS criteria.

Intercurrent events are addressed as follows:

- Scans following randomised study intervention discontinuation will not be included in the analysis, assuming a while-on-treatment strategy to the intercurrent event of randomised study intervention discontinuation (including early crossover from placebo and progression) prior to end of cycle 16 due to any reason.
- Scans following the first 28 days of a prolonged study intervention interruption (defined as a study intervention interruption greater than or equal to 28 days) until study intervention has recommenced for at least 28 days will not be included in the analysis, assuming a while-on-treatment strategy to the intercurrent event of prolonged study intervention interruption.
- Scans after target PN surgical resection will be included in the analysis assuming a treatment policy approach to the intercurrent event of target PN resection.
- Scans after subsequent NF1-PN treatment will not be included in the analysis assuming a while-on-treatment strategy to the intercurrent event of subsequent NF1-PN treatment.

The primary endpoint ORR will be compared at the landmark end of Cycle 16 between selumetinib versus placebo using a Fisher's exact test. ORR in each treatment group will be presented with corresponding two-sided exact 95% confidence interval (CI) based on the Clopper-Pearson method ([Clopper and Pearson 1934](#)). The risk difference and 95% CI based on the Miettinen-Nurminen (score) method ([Miettinen and Nurminen 1985](#)) will also be presented.

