#### Type of Participant and Disease Characteristics

- 2 All participants must have a diagnosis of NF1 with symptomatic, inoperable PN where:
  - (a) Participants must have PN and at least one other diagnostic criterion for NF1 ([Legius et al 2021](#)):
    - (i) Six or more café-au-lait spots ( $> 5$  mm in greatest diameter in pre-pubertal participants or  $> 15$  mm in greatest diameter in post-pubertal participants)
    - (ii) Freckling in the axillary or inguinal region
      - At least one of the two pigmentary findings (café-au-lait macules or freckling) should be bilateral
    - (iii) Two or more iris Lisch nodules identified by slit lamp examination or 2 or more choroidal abnormalities—defined as bright, patchy nodules imaged by optical coherence tomography/near-infrared reflectance imaging
    - (iv) Optic pathway glioma
    - (v) A distinctive osseous lesion such as: sphenoid dysplasia, anterolateral bowing of the tibia, or pseudoarthrosis of a long bone
      - Sphenoid wing dysplasia is not a separate criterion in case of an ipsilateral orbital PN.
    - (vi) A NF1 heterozygous pathogenic variant with a variant allele fraction of 50% in apparently normal tissue such as white blood cells

(vii) A parent with NF1 by the above criteria

(b) A PN is defined as a neurofibroma that has grown along the length of a nerve and may involve multiple fascicles and branches. A spinal PN involves 2 or more levels with connection between the levels or extending laterally along the nerve. A histologic confirmation of the PN is not necessary in the presence of consistent clinical and radiographic findings, but should be considered if malignant transformation of a PN is clinically suspected.

(c) Inoperable is defined as a PN that cannot be completely surgically removed without a risk of substantial morbidity (including significant bleeding or damage to nerves and/or surrounding vital structures) due to encasement of, or close proximity to, vital structures, invasiveness, or high vascularity of the PN; or unacceptable risk from the general anaesthetic as assessed by the investigator.

(d) Symptomatic is defined as clinically significant symptoms caused by the PN, as judged by the investigator; symptoms may include, but are not limited to, pain, motor dysfunction, and disfigurement.

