3 Participants must have completed a pain diary (PAINS-pNF) with a documented chronic target PN pain score for at least 4 days out of 7 days for at least 2 weeks during the screening period. Participants must have stable chronic PN pain medication use at baseline, defined as no clinically significant changes to prescribed chronic PN pain medication within 28 days prior to study enrolment or planned at the time of study enrolment.

4 Eastern Cooperative Oncology Group performance status of 0 or 1 with no deterioration over the previous 2 weeks prior to baseline or day of first dosing. Participants who are wheelchair bound because of paralysis secondary to a PN should be considered ambulatory when they are in their wheelchair. Similarly, participants with limited mobility secondary to a need for mechanical support (such as an airway PN requiring tracheostomy or continuous positive airway pressure) will also be considered ambulatory for the purpose of the study.

5 Participants must have at least one measurable PN, defined as a PN of at least 3 cm measured in one dimension, which can be seen on at least 3 imaging slices and have a reasonably well-defined contour. Participants who have undergone surgery for resection of a PN are eligible provided the PN was incompletely resected and is measurable. The target PN will be defined as the clinically most relevant PN, which is measurable by volumetric MRI analysis.

6 Adequate organ and marrow function as follows with no blood transfusions (of red blood cells/other blood products) within 28 days prior to screening assessment and no growth factors within 7 days prior to screening assessment:

- Haemoglobin  $\geq 9.0$  g/dL.
- Absolute neutrophil count  $\geq 1.5 \times 10^9/L$ .

- Platelet count  $\geq 100 \times 10^9/\text{L}$ .
- Total bilirubin  $\leq 1.5 \times \text{ULN}$  or  $\leq 3 \times \text{ULN}$  in the presence of documented Gilbert's syndrome (unconjugated hyperbilirubinemia).
- Alanine aminotransferase and AST  $\leq 2.5 \times \text{ULN}$ .
- Calculated creatinine clearance  $\geq 60 \text{ mL/min}$  as determined by Cockcroft-Gault (using actual body weight).

Males:

$$\text{CrCL} = \frac{\text{Weight (kg)} \times (140 - \text{Age})}{72 \times \text{serum creatinine (mg/dL)}}$$

Females:

$$\text{CrCL} = \frac{\text{Weight (kg)} \times (140 - \text{Age})}{72 \times \text{serum creatinine (mg/dL)}} \times 0.85$$

7 All participants must be able to swallow whole capsules.

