- Complete response: disappearance of the target PN. The CR is considered unconfirmed at first detection and confirmed when observed again at a consecutive scan within 3 to 6 months.

- Partial response: decrease in the volume of the target PN by 20% or more compared to baseline. The PR is considered unconfirmed at the first detection and confirmed when observed again at a consecutive scan within 3 to 6 months.
- Stable disease: insufficient volume change to qualify for either PR or PD.
- Progressive disease: increase in the volume of the target PN by 20% or more compared to baseline or the time of best response after documenting a PR. The appearance of new PN (with the exception of new discrete subcutaneous neurofibromas as noted below) which is unequivocally and completely distinct and separate from the target PN and the non-target PN, or unequivocal progression of an existing non-target PN is also considered PD. In this study unequivocal progression is defined as an increase in the volume of the non-target PN by 20% or more compared to baseline.

The clinical appearance of new discrete subcutaneous neurofibromas does not qualify for disease progression.

Before submitting the MRI scans to the central review vendor site staff should ensure that the target PN and non-target PN (if applicable) are fully visible on the scans.

In the event that a participant taking part in the study had a target PN resection and remained in the study, MRI scans will continue to be collected.

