4.2.1.6 MRI Assessments During Prolonged Study Intervention Interruption

Patients may require prolonged interruption of treatment to undergo a surgery or manage treatment toxicity. A prolonged study intervention interruption is defined as greater than 28 continuous days of no study intervention.

If a while-on-treatment strategy to prolonged study intervention interruption is chosen, the following rules will be applied for MRI volumetric assessments performed during a prolonged interruption of the study intervention prior to the derivation of the target PN response:

- Any MRI assessments performed within the first 28 continuous days of prolonged study intervention interruption will be included in the analysis.
- Any MRI assessments performed after the first 28 continuous days of study intervention interruption and during ongoing prolonged study intervention interruption will be excluded from the analysis.
- Any MRI assessments performed at a timepoint when the patient has received less than 28 days of study intervention since study intervention recommencing following the prolonged study intervention interruption will be excluded from the analysis.
- Any MRI assessments performed at a timepoint when the patient has received greater than or equal to 28 days of study intervention since study intervention recommencing will be included in the analysis.

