4.2.1.7 Intercurrent Events

The intercurrent event strategy for the primary estimand is described in [Table 8](#).

Table 8: Intercurrent Event Strategy for Primary Estimand

Intercurrent event	Strategy	Details
Post randomised study intervention discontinuation (including early crossover from placebo ¹ and progression) prior to the	While on-treatment strategy	Scans after the randomised study intervention discontinuation will not be included in the analysis.

end of cycle 16 due to any reason		
Prolonged study intervention interruption (greater than 28 days ²)	While on-treatment strategy	Scans after the first 28 days of a prolonged study intervention interruption until study intervention has recommenced for at least 28 days will not be included in the analysis. See Section 4.2.1.6 for further details.
Target PN resection	Treatment policy strategy	Scans after a target PN resection will be included in the analysis.
Subsequent NF1-PN treatment	While on-treatment strategy	Scans after subsequent NF1-PN treatment will not be included in the analysis.

¹ Crossover from placebo to selumetinib prior to Cycle 12 in case of progression on imaging as determined by ICR per REiNS criteria.

² 28 Continuous days of no study intervention

NF1, neurofibromatosis type 1; PN, plexiform neurofibroma.

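### Does the primary ORR need a planned analysis that leaves out scans taken after resection of the target PN?

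*Protocol*

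**What the plan says.** The treatment of resection is the same wherever the primary estimand is described. The protocol synopsis (Primary Estimand) says "Scans after target PN surgical resection will be included in the analysis", Protocol 9.4.2.1.3 says "Scans after target PN resection will be included in the analysis assuming a treatment policy approach to the intercurrent event of target PN resection", and Table 8 in SAP 4.2.1.7 has "Scans after a target PN resection will be included in the analysis".

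Four other provisions bear on the point.

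- **Derivation of response.** Under Protocol 9.4.2.1.1, target PN response "will be programmatically derived from the percentage change in target PN volume". SAP 4.2.1.2 uses the same volume thresholds. Neither makes an exception for surgery.
- **Imaging.** Protocol 8.1.1 provides that if a participant "had a target PN resection and remained in the study, MRI scans will continue to be collected".
- **Eligibility.** Criterion 2(c) in Protocol 5.1 reads "Inoperable is defined as a PN that cannot be completely surgically removed without a risk of substantial morbidity". Criterion 5 adds "Participants who have undergone surgery for resection of a PN are eligible provided the PN was incompletely resected and is measurable". Exclusion 16 in Protocol 5.2 rules out anyone expected to need major surgery during the study.
- **Interruption.** SAP 4.2.1.6 recognises that "Patients may require prolonged interruption of treatment to undergo a surgery or manage treatment toxicity". It drops scans taken after the first 28 days off drug until dosing has resumed for 28 days. SAP 4.2.1.8 treats a dropped scan as a missed visit, which breaks confirmation.

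**The concern.** A partial response is a fall of at least 20% in target PN volume, confirmed on the next scan. Debulking surgery can produce that fall with no drug effect. Criterion 2(c) excludes only safe complete removal, and criterion 5 accepts that an incompletely resected PN can be measured, so a partly resected target could still give evaluable volumes. A participant who stays on treatment and has two qualifying scans by end of Cycle 16 would be counted as a responder, in either arm.

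The result will be read as drug-induced shrinkage against a placebo rate that Protocol 9.2 takes to be 0%. That figure rests on unconfirmed post-crossover responses and the absence of spontaneous shrinkage; surgery is not considered. If surgical responses occurred, no planned table would separate them from drug responses.

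**Working it through.** **Which planned analyses touch resection?** Each was checked in turn.

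| Analysis | What it varies | Excludes post-resection scans? |
|---|---|---|
| Protocol 9.4.2.1.3, supplementary | Population (FAS, now the primary set in the SAP) | No |
| SAP 4.2.1.10, sensitivity | Puts interruption scans back | No |
| SAP 4.2.1.11, partial volumes | Handling of partial volumes after DCO1 | No |
| SAP 4.2.1.11, volumes over time and BOR | Descriptive summaries; BOR under Table 8 | No |
| SAP 4.2.3.3 to 4.2.3.5, single-arm ORR | Interruption scans, analysis set | No |

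The gap is therefore as described. The information is still available: procedures are listed (SAP 4.1.8.2), individual target volumes are plotted (SAP 4.2.1.11) and target PN visit responses are listed (SAP 4.2.18.4).

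**The plan's own figure.** Protocol 9.2 gives more than 99% power for 20% v 0% with 73 per arm and a two-sided Fisher's exact test at 5%. Exact enumeration gives 99.83%, at 0.05 and at 0.047 alike, so the figure reproduces.

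**DCO2.** Inputs: 73 per arm (Protocol 9.2) and alpha 0.047 (Protocol 9.1). Planned selumetinib responders: 0.20 × 73 = 14.6, taken as 15. Placebo: 0. All p-values are two-sided Fisher.

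| Selumetinib v placebo | p |
|---|---|
| 15 v 0 | 0.00003 |
| 14 v 0; 13 v 0; 12 v 0 | 0.00006; 0.00014; 0.0003 |
| 6 v 0 | 0.028 |
| 5 v 0 | 0.058 |
| 15 v 1; 15 v 2; 15 v 3 | 0.0003; 0.0013; 0.0044 |
| 15 v 5 | 0.028 |
| 15 v 6 | 0.057 |

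Reclassifying surgical responders on selumetinib overturns the result only at 15 − 5 = 10 of them. Counting placebo resections as responses overturns it only at six.

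**Type I error at DCO2.** Suppose, as an assumption, that there is no drug effect and the same share of each arm is scored through resection. The rejection rate at 0.047 is 1.4% if that share is 5%, and 0.2% if it is 2%. Both are well below the nominal level.

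**DCO1.** Inputs: the 100th randomised participant and 1:1 allocation, so about 50 per arm; alpha 0.003. Planned responders: 0.20 × 50 = 10.

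| Selumetinib v placebo | p | Against 0.003 |
|---|---|---|
| 8 v 0 | 0.0058 | not met |
| 9 v 0 | 0.0026 | met |
| 10 v 0 | 0.0012 | met |
| 10 v 1 | 0.0078 | not met |

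One case can move the decision in either direction, as one response of any origin would near so small a threshold.

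**When could a resection count?** Scans fall on Days 112, 224, 336 and 448. Assume the dosing gap starts at surgery and require two consecutive included scans afterwards. With a gap under 28 days, resection on 335 of 448 days could count (75%). With a 42-day gap it is 294 of 448 (66%), and with a 56-day gap 280 of 448 (63%). The interruption rule narrows the route without closing it. These are timing windows only; they say nothing about how often a resection happens or shrinks the volume by 20%.

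**The case for a change.** The sponsor treats resection as plausible enough to name it as an intercurrent event for the primary and both key secondary estimands, and the latest protocol amendment added text on continued scanning after it. Prolonged interruption has its own sensitivity analysis, and responses after subsequent NF1-PN treatment are removed from the numerator. Resection acts directly on the quantity being measured, yet has neither safeguard. One case could decide DCO1, whose results may support a submission (Protocol 9.5). Specifying the analysis before unblinding would avoid a post hoc one.

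The description of the gap stands in full, and so does the asymmetry with interruption. The inference that the plan is deficient does not. Under treatment policy, response regardless of resection is the target, and post-resection scans are observed data, so there is no missing-data assumption to stress. An analysis without them answers a different question. The SAP amendment history also records a deliberate cut in supplementary analyses of the primary endpoint to keep interpretation simple.

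The DCO1 point is mostly about the size of the interim alpha. A miss there sends the test to DCO2, and DCO1 may be skipped if the two cut-offs are within about four months.

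Nor is the addition certain to be cost-free. The SAP says procedures are MedDRA-coded and listed, but shows no flag or date for resection of the target PN specifically.

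**Conclusion.** No change to the plan is needed. Scans after target PN resection stay in every planned ORR and best-response analysis, and no table counts resected responders by arm. That follows from a consistently stated treatment-policy strategy, and the plan followed as written still supports a sound conclusion. At the planned rates the DCO2 result survives up to nine surgical responders among the 15 on selumetinib, or up to five on placebo, and type I error stays below its nominal level.

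This rests on resections being few, which the inoperability criterion and the exclusion of anticipated major surgery make likely but the documents do not quantify. It also rests on the listings and individual plots being enough to trace those cases. Two things remain unknown: whether central review returns an evaluable volume for a resected PN, which would be in the independent review charter, and what the interim analysis SAP provides. Neither document was available. If resections do occur, a count by arm with the affected responders named would be a sensible descriptive note in the report. It is optional, and extending it to single-arm ORR, BOR or best percentage change would add nothing to the confirmatory conclusion.
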